5.1 Inclusion criteria

Patients eligible for inclusion in this study must fulfill all of the following criteria:

1. Patient must be able to understand and communicate with the investigator and comply with the requirements of the study and must provide written, signed and dated informed consent before any study assessment is performed.
2. Male or non-pregnant, non-lactating female patients at least 18 years of age.
3. Diagnosis of axSpA (either r-axSpA (AS) or nr-axSpA) fulfilling the ASAS classification criteria for axSpA ([Appendix 2](#)).
4. Active disease as defined by having an ASDAS ≥ 2.1 at Screening and Baseline despite concurrent NSAID therapy, or intolerance/contraindication to NSAIDs.
5. Objective signs of inflammation at Screening as defined by:
MRI of sacroiliac joints performed up to 3 months prior to screening showing acute inflammatory lesion(s),
OR
elevated quick CRP (> 5 mg/L),
OR
MRI showing acute inflammatory lesion(s) in the sacroiliac joints performed during screening period.
6. Patients should have been on at least 2 different NSAIDs at the highest recommended dose for at least 4 weeks (in total) in the past, with an inadequate response or failure to respond, or less if therapy had to be reduced due to intolerance, toxicity or contraindications.
7. Patients who are regularly taking NSAIDs (including cyclooxygenase-1 [COX-1] or cyclooxygenase-2 [COX-2] inhibitors) as part of their axSpA therapy are required to be on a stable dose for at least 1 week before randomization.
8. Patients taking MTX (7.5 mg/week to 25 mg/week) or sulfasalazine (≤ 3 g/day) are allowed to continue their medication but are required to be on a stable dose for at least 4 weeks before randomization.
9. Patients who are on a DMARD other than methotrexate (MTX) or sulfasalazine must discontinue the DMARD 4 weeks prior to randomization.
10. Patients taking corticosteroids must be on a stable dose of ≤ 10 mg/day prednisone or equivalent for at least 2 weeks before randomization and should remain on a stable dose up to Week 24.

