10.1 Definition of adverse events and reporting requirements

10.1.1 Adverse events

An AE is any untoward medical occurrence (e.g. any unfavorable and unintended sign [including abnormal laboratory findings], symptom or disease) in a patient or clinical investigation patient after providing written informed consent for participation in the study. Therefore, an AE may or may not be temporally or causally associated with the use of a medicinal (investigational) product. In addition, all reports of intentional misuse and abuse of the study treatment are also considered an AE irrespective if a clinical event has occurred. See [Section 10.1.5](#) for an overview of the reporting requirements.

The investigator has the responsibility for managing the safety of individual patient and identifying AEs.

Novartis qualified medical personnel will be readily available to advise on trial related medical questions or problems.

The occurrence of AEs must be sought by non-directive questioning of the patient at each visit during the study. Adverse events also may be detected when they are volunteered by the patient during or between visits or through physical examination finding, laboratory test finding, or other assessments.

Adverse events must be recorded under the signs, symptoms or diagnosis associated with them, accompanied by the following information (as far as possible) (if the event is serious refer to [Section 10.1.3](#)):

1. The severity grade:
 - Mild: Usually transient in nature and generally not interfering with normal activities
 - Moderate: Sufficiently discomforting to interfere with normal activities
 - Severe: Prevents normal activities
2. Its relationship to the investigational treatment and other treatment. If the event is due to lack of efficacy or progression of underlying illness (i.e. progression of the study indication) the assessment of causality will usually be 'not suspected.' The rationale for this guidance is that the symptoms of a lack of efficacy or progression of underlying illness are not caused by the trial drug, they happen in spite of its administration and/or both lack of efficacy and progression of underlying disease can only be evaluated meaningfully by an analysis of cohorts, not on a single patient.
3. Its duration (start and end dates) or if the event is ongoing an outcome of not recovered/not resolved must be reported.

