2.1.1 General definitions

Study treatment: Study treatment refers to:

1. Investigational treatment Treat to Target (T2T) = secukinumab 150 mg and/or 300 mg and/or adalimumab biosimilar 40 mg (GP2017)
2. Standard of Care (SOC) treatment up to the maximum recommended dose at the discretion of the investigator

The **treatment phase** is defined as the period from randomization until end of the last treatment period with treatment periods defined as:

- Period 1: date of randomization until day before visit Week 12
- Period 2: date of visit Week 12 until day before visit Week 24

- Period 3: date of visit Week 24 until day before visit Week 36

The following exceptions are made to these definitions:

- If visit Week 12 or 24 is missing but the next visit is documented, the visit date is interpolated in the middle between the earlier and the later visit.
- End dates of period 1, 2, 3: If no further visit was performed during the treatment phase after start of the period, the end date is set to the documented end of treatment date or to the period start date, if no treatment was applied in this period.
- End date of period 3: If the documented end of treatment date is on visit Week 36 date or later, the end date of period 3 is set to the end of treatment date.
- Treat-to-Target group: If treatment was not applied at visit Week 12 or 24, or the last dose of the previous period was still applied on the date of visit, the start date of period 2 resp. 3 is set to the date of first dose in this period. Cases where the last dose of the previous period was still applied on the visit date are identified by the same dose as in the previous period applied on the visit date, but treatment was switched at the first dose after the visit.

Treat-to-Target regimen

Starting from Baseline, subject will be treated with secukinumab 150 mg subcutaneous (s.c.) weekly until Week 4 and then at Week 8.

At Week 12

- If the subject achieves and maintains an ASDAS clinically important improvement (i.e. change from Baseline in ASDAS ≥ 1.1 indicating subjects is a responder), then the subject will continue with secukinumab 150 mg s.c. every 4 weeks up to Week 32.
- If the subject did not achieve ASDAS clinically important improvement (i.e. non-responder) then the subject will receive an escalated dose of secukinumab 300 mg s.c. every 4 weeks until Week 20.

At Week 24

Subjects who are receiving secukinumab 300 mg and

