- Achieves ASDAS clinically important improvement (i.e. responder) will continue with secukinumab 300 mg s.c. every 4 weeks up to Week 32.
- Do not achieve ASDAS clinically important improvement (i.e. non-responder), will be switched to adalimumab biosimilar (GP2017) 40 mg s.c. every 2 weeks until Week 34.

Escape arm

- Subjects who are receiving 150 mg secukinumab (i.e. were responders at Week 12) can be escalated at Week 24 to 300 mg secukinumab every 4 weeks until Week 32 if they experience a loss of response, where loss of response is defined as ASDAS change from Baseline <1.1 .

If the ASDAS measurement is missing at a visit, it is assumed that the planned dose continues for the next treatment period.

Standard of Care Regimen

Patients will receive treatment according to local practice standards by their treating physician following the current treatment recommendations with NSAIDs as the first-choice drug treatment and disease-modifying anti-rheumatic drugs (DMARDs) for patients with active disease because of a lack of response, intolerance, or contraindication to NSAIDs ([van der Heijde et al 2017](#)). Patients will be seen every 12 weeks or more often, if clinically indicated up to Week 36; assessment of the outcome parameters will be performed at Week 12, Week 24 and Week 36.

Study treatment (T2T) start and end date: Study treatment start date is defined as the first date of study drug administration and recorded on the Drug Administration Record (DAR) Electronic Case Report Form (eCRF) page. Similarly, study drug end date is defined as the last date of study drug administration and is recorded on the DAR eCRF page.

SOC treatment start and end date: SOC treatment start date is defined as the first date of any SOC drug for AxSPA treatment after randomization. Similarly, SOC drug end date is inferred as the last date of any SOC drug administration for AxSPA treatment within the treatment phase.

Study day: Study Day 1 is defined as the first day of administration of randomized study treatment. Study day will be calculated as (event date – study drug start date + 1 day) for events that occurred on or after study drug start date (e.g. visit, lab samples, AEs). For events prior to study drug start date (e.g. time since diagnosis), study day will be negative and calculated as (event date – study drug start date).

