2.8.1 Adverse events (AEs)

All information obtained on AEs will be displayed by treatment group and subject. Summary tables for AEs will summarize only on-treatment events, with a start date during the on-treatment period (see [Section 2.1.1](#) for definition of on-treatment period).

The count of treatment-emergent AEs, number (and percentage) of subjects with treatment-emergent AEs (defined as events started after the first dose of study treatment or events present prior to start of study treatment but increased in severity based on PT) will be summarized in the following ways:

- By treatment, primary system organ class and PT.
- By treatment, primary system organ class, PT and maximum severity.

Adverse events in the T2T arm will be summarized by 3 groups (secukinumab 150 mg, secukinumab 300 mg and adalimumab 40 mg).

Adverse events occurring in the SOC arm for patients treated with any of the following: secukinumab 150 mg, secukinumab 300 mg, adalimumab 40 mg and other will also be summarized under a separate SOC page.

Separate summaries will be provided for study treatment related AEs, death, SAEs, other significant AEs action taken leading to study drug withdrawn and AEs leading to dose adjustment (dose increase, dose reduce).

Adverse events will be summarized by presenting, for each treatment group, the number and percentage of patients having any AE, having an AE in each primary system organ class and having each individual AE (PT). Summaries will also be presented for AEs by severity and for study treatment related AEs. If a patient reported more than one AE with the same PT, the AE with the greatest severity will be presented. System organ classes will be presented in alphabetical order, preferred terms will be sorted within system organ class in descending frequency of AEs in the T2T treatment group. If a subjects reported more than one AE within the same primary system organ class, the patient will be counted only once with the greatest severity at the system organ class level, where applicable.

For the legal requirements of ClinicalTrials.gov and EudraCT, 2 required tables on treatment emergent AEs which are not serious adverse events with an incidence greater than 5% and on treatment emergent SAEs and SAEs suspected to be related to study treatment will be provided by system organ class and PT on the safety set population.

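### Study treatment means the biologics alone in T2T but the whole regimen in SOC, so the by-arm related-AE and withdrawal tables do not share one scope

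*SAP*

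**What the plan says.** SAP 2.1.1 gives study treatment two meanings. In T2T it is "Investigational treatment Treat to Target (T2T) = secukinumab 150 mg and/or 300 mg and/or adalimumab biosimilar 40 mg (GP2017"). In SOC it is "Standard of Care (SOC) treatment up to the maximum recommended dose at the discretion of the investigator". The same section describes the SOC regimen as "following the current treatment recommendations with NSAIDs as the first-choice drug treatment and disease-modifying anti-rheumatic drugs (DMARDs"), and dates it broadly: "SOC treatment start date is defined as the first date of any SOC drug for AxSPA treatment after randomization".

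T2T patients may take the same background drugs. Protocol 5.1 admits "Patients who are regularly taking NSAIDs (including cyclooxygenase-1 [COX-1] or cyclooxygenase-2 [COX-2] inhibitors) as part of their axSpA therapy", provided the dose is stable. It says of patients on methotrexate or sulfasalazine that they "are allowed to continue their medication but are required to be on a stable dose for at least 4 weeks before randomization". Low-dose corticosteroids at a stable dose are also allowed. Protocol 6.2.3 treats NSAIDs, non-biologic DMARDs and corticosteroids as concomitant therapy.

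On the output side, SAP 2.8.1 states: "Separate summaries will be provided for study treatment related AEs, death, SAEs, other significant AEs action taken leading to study drug withdrawn". It adds AEs leading to dose adjustment, registry tables that include SAEs suspected to be related to study treatment, deaths from such SAEs, and a summary of action taken. For causality, Protocol 10.1.1 asks the investigator to record "Its relationship to the investigational treatment and other treatment"; it asks for action taken in the same two parts.

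**The concern.** A by-arm table of related events is readable only if related means the same in both columns. Here the SOC column covers events attributed to any axSpA drug, and the T2T column covers only those attributed to secukinumab or adalimumab. Two patients with the same NSAID-attributed gastric event would be classified differently because of their arm.

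The trial is open-label, and safety and tolerability of secukinumab is a stated secondary objective. Tables of related events and withdrawals are what many readers use to judge tolerability. If the columns differ in scope, a difference between them can be an artefact of the definition.

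**Working it through.** The plan gives no AE rates, so there is no figure of its own to reproduce on this point. The check is a trace of definitions, followed by an illustration under stated assumptions.

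**1. Scope by arm**

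| Drug | T2T | SOC |
|---|---|---|
| Secukinumab, adalimumab | Study treatment (SAP 2.1.1) | Study treatment if given as SOC |
| NSAIDs | Permitted, concomitant (Protocol 5.1, 6.2.3) | Study treatment (SAP 2.1.1) |
| Methotrexate, sulfasalazine | Permitted, concomitant (Protocol 5.1, 6.2.3) | Study treatment |
| Corticosteroids for axSpA | Permitted within limits, concomitant (Protocol 5.1, 6.2.1.1) | Study treatment |
| Other csDMARDs | Protocol deviation (Table 6-2) | Study treatment, unrestricted |

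The asymmetry for drugs permitted in both arms is in rows 2 to 4.

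**2. Related AEs, SAEs and deaths.** SAP 2.8.1 uses the defined term *study treatment* for these. An event attributed to a drug in rows 2 to 4 is inside the SOC table and outside the T2T table.

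**3. Withdrawal, dose adjustment and action taken.** The withdrawal and action-taken outputs depend on *study drug*, which has no single meaning. SAP 2.1.1 ties its start and end dates to the T2T drug administration record and speaks of SOC drugs separately. SAP 2.4.1 uses it in the exposure formula for T2T, SOC, Other and Overall. On the wide reading, SOC events are counted on a broader scope than T2T events. On the narrow reading, SOC events are undefined or fall under not applicable, a category in the action-taken summary. The dose-adjustment table does not name its drug and inherits the same doubt. The columns do not match on either reading.

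**4. Is it repaired elsewhere?** SAP 2.8.1 splits T2T events by secukinumab 150 mg, secukinumab 300 mg and adalimumab, and has a separate SOC page by the same three plus other. T2T has no matching category for background drugs. The AE listing gives relationship to, and action with, study drug only. No SAP output uses the other-treatment items of Protocol 10.1.1, and SAP Section 4 records no change or caveat.

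**5. Illustration (all rates assumed).** Let *u* be the share of patients on an NSAID or csDMARD, *r* the risk among them of an AE attributed to it, and *b* the risk of an AE attributed to a biologic. All are equal in both arms, and the two kinds of event are independent.

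- T2T table = b
- SOC table = 1 − (1 − u·r)(1 − b)
- Gap = u·r·(1 − b)

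| u | r | b | SOC table | T2T table | Gap (points) | Gap × 150 patients |
|---|---|---|---|---|---|---|
| 0.4 | 0.05 | 0.20 | 21.6% | 20% | 1.6 | 2.4 |
| 0.8 | 0.10 | 0.20 | 26.4% | 20% | 6.4 | 9.6 |
| 0.4 | 0.20 | 0.10 | 17.2% | 10% | 7.2 | 10.8 |
| 0.8 | 0.20 | 0.10 | 24.4% | 10% | 14.4 | 21.6 |

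The first and last rows are the extremes over u of 0.4 or 0.8, r of 0.05, 0.10 or 0.20, and b of 0.10 or 0.20. The table shows only that the definition can create a gap when true harm is equal.

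**The case against.** Several points on the other side have force.

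- **The safety endpoint is all-cause.** Protocol Table 2-1 and SAP Table 1-1 name the number and percentage of patients with treatment-emergent AEs. The objective is not superiority over SOC on related events, and SAP 2.8 plans no between-arm safety test. This stands and limits the consequence.
- **Direction.** A reader might infer that every affected table favours T2T. The documents do not support that. If *study drug* means only the drugs on the T2T record, SOC withdrawals could be missing altogether and the imbalance would run against T2T.
- **Stopping one NSAID.** It is tempting to count this as a withdrawal in SOC. But SOC is a regimen in which switching is expected (Protocol 6.1), and no passage says that changing one component is withdrawal of SOC treatment. This stands.
- **Equal background use.** Table 6-2 discourages dose increases of NSAIDs, methotrexate and sulfasalazine in T2T. SOC has no prohibited concomitant treatment and may go up to the maximum recommended dose. Biologic use may differ too. Part of any SOC excess could therefore be a real regimen difference, so the illustration is not an estimate.
- **The SOC page by drug.** It separates SOC patients on the named biologics from the rest, which helps, but T2T has no matching column.
- **Biologic-only attribution may be intended.** If so, it should apply in both arms. As defined, it applies in one.
- **The eCRF is not visible.** Protocol 10.1.1 does not prove that two separate fields exist, and other treatment in the glossary covers concomitant and rescue therapy generally. This stands and bears on the fix.

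**Conclusion.** The point holds with limits. On the SAP's own definition, the by-arm tables of study-treatment-related AEs, related SAEs and related deaths include events attributed to NSAIDs, methotrexate, sulfasalazine or corticosteroids in SOC and exclude them in T2T. This rests on SAP 2.8.1 using *study treatment* as SAP 2.1.1 defines it. The withdrawal, dose-adjustment and action-taken tables are also not comparable, but for a different reason: the term is ambiguous for SOC, and the direction is open.

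All-cause AE, SAE and death tables are not affected through attribution. A reader might go further and conclude that the safety comparison as a whole is biased, or take the 1.6 to 14.4 points as the expected error. Neither follows: the stated endpoint does not use attribution, and the range comes entirely from assumed rates and equal drug use.

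**What to change.** In SAP 2.8.1, present the by-arm related, withdrawn, dose-adjustment and action-taken tables on one scope in both arms. Use the relationship and action items for both investigational and other treatment (Protocol 10.1.1), linked to axSpA medication where the eCRF allows. State what *study drug* means for SOC patients. Keep a biologic-only display as a second table, with that scope applied to both arms.

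If the eCRF cannot support this, base the between-arm comparison on all-cause AEs and label the related and withdrawn tables as not comparable between arms.

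The cost is SAP wording and some extra programming; no treatment or conduct rule changes. T2T figures may look slightly less favourable. If other treatment is a single field, a few events attributed to drugs not given for axSpA may enter the tables in both arms.

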2.8.1.1 Adverse events of special interest / grouping of AEs

Not applicable.

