Neutropenia was more frequently observed with secukinumab than with placebo, but most cases were mild, transient, and spontaneously reversible.

The incidence of hypersensitivity AEs was slightly higher with secukinumab compared with placebo, with the difference mostly due to mild to moderate urticaria and eczema not associated with systemic symptoms.

The incidence of selected rare events of interest (major adverse cardiovascular events and malignancies) adjusted for exposure over 52 weeks was comparable to placebo in clinical trials across multiple indications.

There was no clear association between treatment with secukinumab and new onset of inflammatory bowel disease but due to the potential involvement of the interleukin-17 (IL-17) pathway in the pathogenesis of the disease, it is not possible to rule out a potential increased risk of exacerbation.

Secukinumab 300 mg was comparable to 150 mg and both doses showed comparable safety to placebo and etanercept over 52 weeks of treatment.

Infections, neutropenia, and hypersensitivity are important identified risks, while malignancies, major adverse cardiovascular events, immunogenicity, Crohn's disease, and hepatitis B reactivation are important potential risks. Interaction with live vaccines is an important potential interaction (and also included as an important potential risk).

No new identified risks were reported. During the reporting interval, a Risk Management Plan (RMP) update was triggered upon request from Pharmacovigilance Risk Assessment Committee, to include suicidal ideation and behavior (SIB) as an important potential risk in the RMP on the basis that "although causality has not been established, SIB meets the criteria as important potential risk because a potential biological mechanism cannot be completely ruled out since the biological role of IL-17 receptor ligands is still largely unknown, and consideration of the potential public health impact". The RMP is currently being updated for this change. At its completion SIB will be listed as an important potential risk in the RMP.

No new safety signal was identified and no actions were taken for safety reasons during the reporting period of the latest drug safety update report.

The risk to patients in this trial will be minimized by compliance with the eligibility criteria, close clinical monitoring, and extensive guidance to the investigators, provided in the current version of the Investigator's Brochure (IB).

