12.5.2 Analysis of secondary safety endpoints

For all safety analyses, the Safety Set will be used. All listings and tables will be presented by treatment group.

Safety summaries (tables, figures) will include only data from the on-treatment period with the exception of Baseline data, which will also be summarized where appropriate (e.g. change from Baseline summaries). In addition, a separate summary for death including on-treatment and post-treatment deaths will be provided. In particular, summary tables for AEs will summarize only on-treatment events, with a start date during the on-treatment period (i.e. treatment-emergent AEs as defined below).

The on-treatment period lasts from the date of first administration of study treatment to 30 days after the date of the last actual administration of any study treatment.

Adverse events

All information obtained on AEs will be displayed by treatment group and patient.

The number (and percentage) of patients with treatment-emergent AEs (defined as events started after the first dose of study medication or events present prior to start of study treatment but increased in severity based on PT) will be summarized in the following ways:

- By treatment, primary system organ class and PT.
- By treatment, primary system organ class, PT and maximum severity.
- By treatment, standardized MedDRA query and PT.

Separate summaries will be provided for study medication related AEs, death, SAEs, other significant AEs leading to discontinuation, AEs leading to dose adjustment and AE of special interest.

Adverse events will be summarized by presenting, for each treatment group, the number and percentage of patients having any AE, having an AE in each primary system organ class and having each individual AE (PT). Summaries will also be presented for AEs by severity and for study treatment related AEs. If a patient reported more than one AE with the same PT, the AE with the greatest severity will be presented. If a patient reported more than one AE within the same primary system organ class, the patient will be counted only once with the greatest severity at the system organ class level, where applicable. Serious adverse events will also be summarized.

Vital signs

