2.13 Other Exploratory analyses

Not applicable.

3 Sample size calculation

The sample size was calculated based on the primary efficacy variable ASAS40 response at Week 24 for the FAS. Available data from the DESIR cohort ([Molto et al 2014](#)) and the DANBIO registry ([Glintborg et al 2017](#)) showed an ASAS40 response of 30% in TNF α inhibitor naïve axSpA subjects, that were treated with common *biological* DMARDs.

Data from MEASURE 2/MEASURE 3 trials ([Sieper et al 2017](#), [Pavelka et al 2017](#)) showed an ASAS40 response of 43.2% and 43.9% at Week 16, while approximately 50% of subjects did not achieve an ASDAS clinically important improvement (defined as change from BSL of ≥ 1.1) criterion at Week 12. Taking into account the longer duration of active treatment with secukinumab 150 mg and the substantial proportion of subjects that will be escalated to 300 mg, it is justifiable to conservatively assume an ASAS40 response of 50% at Week 24.

With an ASAS40 response of 50% for the secukinumab 150 mg/300 mg arm and a 30% response in the SOC arm at Week 24 (corresponding to an OR of 2.3), 134 subjects per treatment arm are required to achieve a power of 90% to demonstrate superiority at a significance level of 0.05 using the 2-group continuity corrected χ^2 test of equal proportions.

In order to account for some uncertainties in the underlying assumptions and to compensate for some expected dropout and protocol violations, a total of 300 subjects (150 patients in the T2T and 150 patients in the SOC arm) should be randomized into this study.

4 Change to protocol specified analyses

Not applicable.

5 Appendix

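### The SAP omits the SMQ tabulation and the special-interest adverse event summary that Protocol 12.5.2 requires, and its Section 4 declares no change

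*SAP*

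**What the plan says.** Protocol 12.5.2 lists three ways in which treatment-emergent AEs will be summarized. The third is "By treatment, standardized MedDRA query and PT". It then lists separate summaries to be provided, ending with "other significant AEs leading to discontinuation, AEs leading to dose adjustment and AE of special interest". Neither item is conditional.

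SAP 2.8.1 follows the same structure. Its list of tabulations stops at the second item, "By treatment, primary system organ class, PT and maximum severity", and its list of separate summaries stops at dose adjustment. SAP 2.8.1.1, under the heading "Adverse events of special interest / grouping of AEs", has a one-line body saying that it does not apply. SAP Section 4, "Change to protocol specified analyses", has the same one-line body. The SAP introduction nevertheless names Section 12 of the protocol as the description of the planned analysis.

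Protocol 4.4 sets out the safety topics for secukinumab. It states that "Infections, neutropenia, and hypersensitivity are important identified risks". It names malignancies, major adverse cardiovascular events, immunogenicity, Crohn's disease and hepatitis B reactivation as important potential risks. It also mentions interaction with live vaccines, and says suicidal ideation and behavior is being added.

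**The concern.** The SAP says it implements the protocol's analysis section, yet it leaves out two safety summaries that the section requires and says nothing has changed. A reader who relies on Section 4 to find departures from the protocol would miss both.

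Safety and tolerability of secukinumab is a secondary objective. Some of the known topics do not sit in one preferred term. Protocol 4.4 says the excess of hypersensitivity events was mostly urticaria and eczema, and it describes Candida infections as both mucosal and cutaneous. A grouped count shows how many patients had any event of the kind, which is what an SMQ or AESI table is for. The trial is open-label, so a grouping chosen after the data have been seen carries less weight than one fixed in the SAP.

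**Working it through.** No figure in the plan depends on this point, so the check compares the texts and then looks at what the SAP still provides.

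**Step 1. The two AE lists side by side**

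| Item | Protocol 12.5.2 | SAP 2.8.1 / 2.8.1.1 |
|---|---|---|
| System organ class and preferred term | yes | yes |
| The same, with maximum severity | yes | yes |
| SMQ and preferred term | yes | absent; SMQ is not named anywhere in the SAP |
| Related AEs | yes | yes |
| Deaths | yes | yes |
| Serious AEs | yes | yes |
| AEs leading to discontinuation | yes | yes |
| AEs leading to dose adjustment | yes | yes |
| AESI | yes | absent from the list; 2.8.1.1 marked not applicable |

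Tabulations: 2 of 3 kept. Separate summaries: 5 of 6 kept. Together, 3 + 6 = 9 items in the protocol and 2 + 5 = 7 in the SAP, so 2 are lost. SAP Section 4 declares 0.

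**Step 2. Is there another explanation?** The relevant text of SAP 2.8.1, 2.8.1.1 and Section 4 is intact, so redaction does not account for the gap. The readable change-history entries for SAP amendments 3.0 (May 2022) and 4.0 (July 2023) mention neither removal. Earlier entries are not in the text available for review. Even if one of them recorded the change, Section 4 would still be wrong.

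**Step 3. What still has an aggregate count**

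- *Infections.* SAP 2.8.1 counts patients with an AE in each primary system organ class. It counts a patient once per class. Assuming that infections form one class in the dictionary, an overall infection count survives.
- *Neutropenia.* SAP 5.4 defines notable neutrophils (below 0.9 times the lower limit of normal) and notable white cells (below 0.8 times). SAP 2.1.2 refers to a summary of notable laboratory abnormalities based on the most extreme value. SAP 2.8.3 adds shift tables by visit and to the most extreme value.

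**Step 4. What does not**

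- *Hypersensitivity.* No grouping is planned. If a patients have one relevant preferred term and b have another, the number with at least one lies anywhere from max(a, b) to a + b, capped at the number in the arm (150 planned). Adding table rows cannot give the patient-level count.
- *Candida infections.* Protocol 4.4 reports no difference between 300 mg and 150 mg in the overall rate of infections, but more Candida infections at 300 mg in the psoriasis trials. On the protocol's own account, the overall infection row is too coarse to show that pattern. This trial uses both doses in the treat-to-target (T2T) arm.
- *Cross-class potential risks.* Major adverse cardiovascular events are the clearest example.

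SAP 2.8.1 also splits the T2T arm into three drug and dose groups, which makes single preferred-term counts smaller still.

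**The case against.** The strongest reply is that little of substance is lost. The declared safety endpoint, the number and percentage of patients with treatment-emergent AEs, is kept. So are the summaries of serious, related and fatal events, of withdrawals and of dose changes, along with a listing of every treatment-emergent AE. Events are MedDRA-coded, so SMQ tables could be produced at any time, and no hypothesis test depends on them. The protocol defines no AESI list and names no SMQ, so the SAP had nothing specific to carry over. All of this is true, and it limits the point to prespecification and consistency of descriptive tables.

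It does not remove the point. The protocol requires both summaries without condition. The missing list is a reason for the SAP, whose purpose is detailed methodology, to supply one. Protocol 4.4 shows that safety topics exist, so the not-applicable entry is not explained by a lack of them.

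Three stronger readings are tempting and should be resisted:

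- A reader might infer that none of the identified risks in Protocol 4.4 has a grouped count. Infections and neutropenia do, as shown above.
- A reader might infer that the SAP expressly rules out the SMQ table. It is left out silently, and 2.8.1.1 reaches it only through the word grouping in its heading.
- A reader might treat Protocol 4.4 as the AESI list. It is a benefit-risk section and is not labelled as such a list. Some entries, such as immunogenicity and live-vaccine interaction, do not translate plainly into grouped AE counts.

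**Conclusion.** The inconsistency is real. Two of nine protocol-specified AE summaries are missing from the SAP, and Section 4 is incorrect in declaring no change. The practical loss falls mainly on hypersensitivity, Candida infections and potential risks that cross system organ classes. It does not extend to infections overall or to laboratory neutropenia. No data are lost, and the primary efficacy analysis is untouched.

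The conclusion that the SAP departs from the protocol rests on the text alone. The judgement of which topics lose most assumes that MedDRA puts infections in one class and spreads hypersensitivity and cardiovascular events over several terms or classes. The documents do not set out the dictionary's structure. The change should be made, but the trial's main conclusions do not depend on it.

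**What to change.** Restore the SMQ tabulation in SAP 2.8.1 and the AESI summary in SAP 2.8.1.1. Fix the list in advance and name the SMQs, using those Protocol 4.4 topics that can be expressed as grouped AE counts. Where no suitable SMQ exists, give an explicit list of preferred terms. Present patient-level counts by arm, as the protocol requires, and preferably also by the three T2T drug groups that SAP 2.8.1 already uses. The latter is a suggestion that goes beyond Protocol 12.5.2.

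If the sponsor decides to drop either summary, SAP Section 4 should say so and give the reason in place of the not-applicable entry.

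The cost is a few additional descriptive tables, or one paragraph in Section 4. AEs are already MedDRA-coded, so there is no new data collection and no change to trial conduct.
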